9.3.4.1 Safety (Objective 1)

Safety outcomes for the Ivacaftor Cohort and the Comparator Cohort will include 6 main categories: death, organ transplantation, hospitalisations, CF complications, and pulmonary exacerbations and respiratory microbiology, and serious safety outcomes (composite outcome). The safety outcomes will be analysed for the Historical Cohort.

1. Death: Frequency of death will be calculated and will include cause of death and age at death. Analyses will be stratified by duration of ivacaftor exposure, age, sex, *CFTR* genotype class, percent predicted FEV₁, and comorbid conditions.
2. Organ transplantations: Frequency of organ transplantations will be calculated and will include type of organ transplanted and age at transplant. Analyses will be stratified by duration of ivacaftor exposure, age, sex, *CFTR* genotype class, percent predicted FEV₁, and comorbid conditions.

3. Hospitalisations: Frequency of hospitalisations will be calculated and will include the number of days of hospitalisation, and age at hospitalisation. Analyses will be stratified by duration of ivacaftor exposure, age, sex, *CFTR* genotype class, percent predicted FEV₁, and comorbid conditions.
4. CF complications: Frequency of CF complications will be calculated. CF complications include infections, arthritis, asthma, bone fracture, diabetes, and several hepatic, gastrointestinal, and pulmonary complications. Analyses will be stratified by duration of ivacaftor exposure, age, sex, *CFTR* genotype class, percent predicted FEV₁, and comorbid conditions.
5. Pulmonary exacerbations and respiratory microbiology: Frequencies of pulmonary exacerbations and respiratory microorganisms will be calculated. Analyses will be stratified by duration of ivacaftor exposure, age, sex, *CFTR* genotype class, percent predicted FEV₁, and comorbid conditions.
6. Serious safety outcomes: Frequency of serious safety outcomes will be calculated. Analyses will be stratified by duration of ivacaftor exposure, age, sex, *CFTR* genotype class, percent predicted FEV₁, and comorbid conditions.

9.3.4.2 Pregnancy (Objective 2)

Frequency and outcomes of pregnancies will be analysed for patients exposed to ivacaftor in the Ivacaftor Pregnancy Cohort and for patients in the Comparator Pregnancy Cohort. Pregnancy outcomes include live birth, stillbirth, spontaneous abortion, therapeutic abortion, undelivered, and unknown. Pregnancy outcomes of gestational age and congenital anomalies of the infant will be described for the CF Trust Patient Registry data. Pregnancies will be described by outcome, age, and duration of ivacaftor exposure. Pregnancy outcomes will also be described for the Historical Cohort.

9.3.4.3 Drug Utilisation (Objective 3)

Drug utilisation of ivacaftor will be described by analysing the Drug Utilisation Cohort. Frequency of ivacaftor exposure by *CFTR* genotype class, age, sex, and percent predicted FEV₁ will be calculated.

A separate description of drug utilisation analyses for other EU patient registries is provided in Annex 3: Additional Information.

9.3.4.4 CF Disease Progression (Objective 4)

In addition to the analyses of death and organ transplant described in Section 9.3.4.1, CF disease progression will be described by analysing the outcomes of CF disease severity and clinical signs of CF disease progression. These outcomes were chosen because they provide the most clinically meaningful description of CF disease progression given the data available in the registries.

CF disease progression will be assessed by comparing changes in health status amongst patients in the Ivacaftor Cohort to those in the Comparator Cohort on relevant disease progression variables. Disease progression variables include CFRD, DIOS, lung disease, and weight and will be assessed annually. Change in disease progression will be assessed when

there are sufficient data available (e.g., change from 2013 health status to 2014 health status will be analysed during 2015).

Health status for CFRD and DIOS will be dichotomous (yes/no or present/absent).

Health status for lung disease severity will be derived from the best annual assessment of percent predicted FEV₁, as

- Mild/Normal if percent predicted FEV₁ ≥70%,
- Moderate if percent predicted FEV₁ is ≥40% to <70%,
- Severe if percent predicted FEV₁ is <40%.²

Percent predicted FEV₁ will be calculated based on the equations of Hankinson et al.³⁰ or Wang et al.³¹ The Hankinson standard will be used for male patients 18 years and older and female patients 16 years and older. The Wang standard will be used for male patients aged 6 to 17 years and for female patients aged 6 to 15 years.

Health status for weight will be based on the relative change from baseline in weight, which will be categorised into meaningful groupings based on the observed results (e.g., -10% to -5%, -5% to 0, 0 to 5%, 5% to 10%). Additionally, for children, percentiles of weight, adjusted for age and height, will be categorised into meaningful groupings. Weight will be explored and included if possible.

In general, the frequency and percentage of patients having each clinical sign (or state if a clinical sign has multiple states possible) will be reported. Shifts in state over time will also be reported. Analyses will be stratified by duration of ivacaftor exposure, age, sex, *CFTR* genotype class, percent predicted FEV₁, and comorbid conditions.

The primary analysis will include only those patients with necessary data points available. The effect of missing data will be assessed with sensitivity analyses, as appropriate.

Analysis of change in lung function over time will be based on percent predicted FEV₁. Descriptive statistics will be presented for the mean at each year and the mean change from Year 1 to the subsequent years. These analyses will include Ivacaftor Cohort patients with evidence of ivacaftor exposure and pulmonary function test results in each of the years in the analysis (e.g., evidence of ivacaftor exposure and FEV₁ results in 2012, 2013, and 2014 for the analysis of change in lung function from 2012 to 2014). Similarly, patients in the Comparator Cohort will include patients with no evidence of ivacaftor exposure in each of the years in the analysis.

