Hospitalisation	start date of hospitalisation for pulmonary exacerbation	start date (any hospitalisation); reason (pulmonary exacerbation, pulmonary complication, GI complication, transplant-related, sinus infection, non-transplant surgery, other)
CF complications	see Section 9.3.1.2	see Section 9.3.2.2
Pulmonary exacerbations and respiratory microbiology ^a	yes/no; respiratory microbiology	yes/no; respiratory microbiology

Table 4 Comparison of Variables Collected by the Patient Registries

Variables	CF Trust (UK)	CF Foundation (US)
Pregnancy	pregnancy occurrence/outcome/undelivered/unknown; gestational age; presence of congenital anomalies at birth; only for female patients 13 years of age and older	pregnancy occurrence/outcome/undelivered/unknown; only for female patients
Serious safety outcomes	combination of death, organ transplantations, hospitalisations, and selected CF complications	combination of death, organ transplantations, hospitalisations, and selected CF complications
Pulmonary function tests ^b	FEV ₁ (L), best FEV ₁ (L), FVC (L), FEF _{25%-75%} (L) during last period, unable to perform test, not done	FEV ₁ (L), FVC (L), FEF _{25%-75%} (L), unable to perform test
Cardiac disease	as reported in CF complication	as reported in reason for hospitalisation or CF complications
Hepatic impairment	reported as liver disease with portal hypertension	reported as liver disease with complications

CF: cystic fibrosis; FEF_{25%-75%}: forced midexpiratory flow; FEV₁: forced expiratory volume in 1 second; FVC: forced vital capacity; GI: gastrointestinal; UK: United Kingdom; US: United States.

^a Whilst the specific respiratory microbiology variables collected by the CF Trust and the CF Foundation differ, efforts will be made to create general categories for the analyses. Details will be provided in the statistical analysis plan.

^b Percent predicted FEV₁ will be calculated based on the equations of Hankinson et al.³⁰ or Wang et al.³¹ The Hankinson standard will be used for male patients 18 years and older and female patients 16 years and older. The Wang standard will be used for male patients aged 6 to 17 years and for female patients aged 6 to 15 years.

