Pregnancy will be defined if there is evidence of pregnancy in the database. Outcomes include live birth, stillbirth, spontaneous abortion, therapeutic abortion, undelivered, and unknown. Note that the CF Foundation Patient Registry does not have a variable of "congenital abnormality" for pregnancy outcome; however, as part of routine pharmacovigilance activities, Vertex collects unsolicited reports of pregnancy using the Pregnancy Safety Information Collection Form (see [Stand-alone Document 4](#) listed in Annex 1. List of Stand-alone Documents). Matching of pregnancy cases between the unsolicited reports and the CF Foundation Patient Registry data will be as thorough as

possible, with considerations for the anonymous nature of the registry data and for patients from the spontaneous reports who may not be in the registry and vice versa.

Cardiac disease will be defined by specification of cardiac disease as a reason for hospitalisation or as a CF complication.

CF lung disease severity will be defined if there is evidence of pulmonary function test results in the database. Absolute measures (in litres) for FEV₁, best FEV₁ during last period, FVC, and FEF_{25%-75%} are collected. Percent predicted values will be calculated based on the equations of Hankinson et al.³⁰ or Wang et al.³¹ (see Section 9.3.4.4). Pulmonary function data are collected at each encounter. On average, there are 5 pulmonary function measures in a calendar year for each patient. In the US, the standard of care for CF includes quarterly office visits to the CF care centre. Best FEV₁ is identified per calendar quarter for each patient.

Clinical signs of CF disease progression will be defined by outcomes previously specified, including death, organ transplantation, and selected CF complications (e.g., CFRD and DIOS).

Change in lung function over time will be defined by pulmonary function test results over the years in the analysis. Absolute measures (in litres) for FEV₁ (current FEV₁ at each encounter) are collected. Percent predicted FEV₁ will be calculated based on the equations of Hankinson et al.³⁰ or Wang et al.³¹ (see Section 9.3.4.4).

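### The lung-severity and shift tables in 9.3.4.4 describe only survivors who could be tested, so unequal loss of sick patients between cohorts would favour the cohort that loses more

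*Protocol*

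**What the plan says.** Protocol section 9.3.4.4 sets up the comparison: "CF disease progression will be assessed by comparing changes in health status amongst patients in the Ivacaftor Cohort to those in the Comparator Cohort". For the lungs, "Health status for lung disease severity will be derived from the best annual assessment of percent predicted FEV"₁, with three classes: mild/normal at 70% or more, moderate from 40% to below 70%, and severe below 40%. No other state exists. The section reports the frequency of each state and adds: "Shifts in state over time will also be reported". The analysis set is then fixed: "The primary analysis will include only those patients with necessary data points available". The only provision for the remaining patients is this: "The effect of missing data will be assessed with sensitivity analyses, as appropriate".

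Two other places bear on the point. Table 4 (section 9.3) shows that an inability to perform the lung function test is a recorded result in both registries. The UK entry lists it apart from a test that was not carried out: "during last period, unable to perform test, not done". Sections 9.3.1.2 and 9.3.2.2 treat death and transplantation as progression: "Clinical signs of CF disease progression will be defined by outcomes previously specified, including death, organ transplantation". Neither the inability to test nor death is given a place in the severity classes.

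**The concern.** A shift needs a class in both years. Under the stated rule, a severe patient who dies before the next year's test has no row in the shift table, and nor does one whose only record for the second year is an inability to perform the test. Percentages such as severe improving to moderate are then calculated among survivors who could be tested.

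Neither loss is ordinary missing data. After death there is no FEV1 to recover, and an inability to perform the test is an observed result. If one cohort loses more of its sickest patients, its remaining patients look healthier, although the protocol itself counts death as progression.

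A related gap concerns lung transplantation. Section 9.3.4.4 does not set recipients apart, so a post-transplant FEV1 could be tabulated as a move from severe to a better class.

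**Working it through.** **Inputs from the protocol**
- Annual death rate in unexposed patients (9.5): 103/9385 = 0.01097, which agrees with the stated 0.011.
- UK completeness (9.6.1): 89% of living patients have an annual encounter, and 95% of those have a lung function measure.
- US completeness (9.6.2): 96% of living nontransplant patients aged 6 or older have a test.

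**Who is outside the table.** UK: 0.89 × 0.95 = 0.8455, so about 15.5% of living patients have no value in a year. US: about 4% of the stated group have none. The completeness figures are for living patients, so deaths come on top. A shift table needs two years and so loses at least as many patients. A patient who dies after an FEV1 in the same calendar year keeps that year's class and drops out the year after.

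**Loss from the severe row through death.** This needs two inputs that the protocol does not give. Assume that the severe class is 8-15% of patients and supplies 60-90% of deaths. Annual loss = share of deaths × 0.01097 / severe share.
- Low end: 0.60 × 0.01097 / 0.15 = 0.044.
- High end: 0.90 × 0.01097 / 0.08 = 0.123.
- Over four years, 1 − (1 − q)^4 gives 16% to 41%.

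**Effect on the severe share.** Assume that 15% of each cohort is truly in the worst condition (severe, unable or dead), and that all dead (d) and unable (u) patients come from that group. The complete-case severe share is (0.15 − d − u) / (1 − d − u). Counting every such patient gives 15.0% in both cohorts in every row.

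| d, cohort A v B | u, cohort A v B | Complete-case severe, A v B | Spurious difference (points) |
|---|---|---|---|
| 1.1% v 1.1% | 0 v 0 | 14.1% v 14.1% | 0 |
| 1.1% v 2.2% | 0 v 0 | 14.1% v 13.1% | −1.0 |
| 1.1% v 3.3% | 0 v 0 | 14.1% v 12.1% | −2.0 |
| 1.1% v 1.1% | 2% v 4% | 12.3% v 10.4% | −1.9 |
| 1.1% v 3.3% | 2% v 4% | 12.3% v 8.3% | −4.0 |

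With equal losses the cohorts do not differ, but both shares are understated.

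**Effect on a shift percentage.** Assume that 15.0% of all starting severe patients improve in each cohort, that 9% die in one and 18% in the other, and that none of the dead would have improved. The complete-case percentages are 15.0/0.91 = 16.5% and 15.0/0.82 = 18.3%. The cohort with twice the deaths shows 1.8 points more improvement. With death as a state, the table reads 15.0% improved in both, and 9% against 18% died.

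**The case against.** The strongest reply is that deaths are already reported where they matter. Section 9.3.4.1 analyses death and transplantation stratified by percent predicted FEV1. Section 9.3.4.4 opens by adding its measures to those analyses and reports each clinical sign by FEV1 stratum. Safety below 40% predicted is a secondary objective under Objective 1 and does not rest on the shift table. All of this stands. A reader might infer that deaths disappear from the study, or that the safety assessment of severe patients would point the wrong way. The protocol supports neither. What remains is that a separate death count does not correct a survivor-only table, and the two could point in opposite directions.

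Second, the effect is small against sampling error. With a severe share of 8-15%, the severe row holds about 35-65 UK patients (from 432) or 83-155 US patients (from 1035). The standard error of a percentage near 18% is then about 3.1-6.6 points, more than the 1.8 points above. This limits the practical weight of the point, but small numbers do not remove a systematic error.

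Third, sensitivity analyses are promised and the detail may be in the SAP. They may help with absent records. But the protocol itself fixes complete cases as the primary analysis, and that table stays conditional on survival and testability whatever the sensitivity analyses show.

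Fourth, it is tempting to read the 4% (US) and 5% (UK) without a test as patients too ill to be tested. They are not counts of such records; they cover every reason for a missing value. Because the class uses the best annual value and US patients average five measures a year, one failed attempt need not remove a patient.

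**Conclusion.** The point holds for the severity frequencies and shift tables of 9.3.4.4. As written, they condition on being alive and having an FEV1 in each year needed, and they drop outcomes that the registries record. The bias between cohorts needs unequal loss. The protocol does not show which cohort would lose more, so it does not follow that the plan favours ivacaftor.

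The size cannot be taken from the document. The loss of about 4-12% of the severe row a year rests on the assumed severe share and share of deaths. The shift of roughly 1-4 points rests on an assumed 15% in the worst condition and on the unequal losses shown. The analysis is descriptive, and no power or alpha figure changes.

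**What to change.** In 9.3.4.4, for the severity frequency and shift tables only:
- Use six states: mild/normal, moderate, severe, unable to perform test (age 6 or older with no valid FEV1 that year), lung transplant, and died. The age limit matches the starting age of the reference equations.
- Take as denominator all patients with a state in the starting year who remain eligible for the cohort.
- Limit the complete-case rule to tests not done or records absent, and show these as a separate column by cohort.
- Add a line on which state counts when a patient qualifies for two in one year, for example an FEV1 followed by death.

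The cost is three more states, from fields that both registries already hold. There are two downsides. Inability to perform the test mixes illness with other reasons, so it should stay its own state and not be merged into severe. Some cells will be small and imprecise.

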9.3.5 Confounders and Effect Modifiers

Other variables, such as duration of prior ivacaftor exposure, pulmonary function, pulmonary microbiology (e.g., *P aeruginosa*), concomitant medications (e.g., dornase alfa, azithromycin), pancreatic sufficiency status, diabetes status, or health care utilisation, will be assessed as confounders and effect modifiers in the statistical analyses through stratification and adjustment, when possible.

9.4 Data Sources

More than 97 paediatric and 35 adult CF care centres in England, Scotland, Wales, and Northern Ireland enter data into the CF Trust Patient Registry database for all patients who consent to participate. More than 110 CF Foundation-accredited care centres in the United States enter data into the CF Foundation Patient Registry for all patients who consent to participate.

All data for the CF Trust and CF Foundation is entered into PortCF, the online registry application, by staff at CF-accredited care centres. Data are entered throughout the year for encounter-based and annual patient visits, whilst summaries of data collected are produced annually (i.e., registry annual reports). Analyses for this PASS will be conducted annually and provided as the yearly reports.

Questionnaires of the CF Trust and CF Foundation patient registries are provided as [Stand-alone Documents 1 and 2](#), respectively (listed in Annex 1. List of Stand-alone Documents). The demographics form captures basic information about the patient, including death date when applicable. The diagnosis form indicates diagnosis and reason for diagnosis and captures genotype testing results. The encounter form is intended to capture data from a clinic visit and includes medications, complications, pulmonary function tests, respiratory microbiology results, laboratory tests, and height and weight. The episode form captures dates and reasons of hospitalisations. The annual review form is a yearly assessment of treatment, transplant status, pregnancy, and socioeconomic data.

For the drug utilisation objective, additional EU-based data sources are under investigation.

9.5 Study Size

The number of patients included in annual analyses will be dependent on the use of ivacaftor amongst patients in the registries. Ivacaftor is indicated for the treatment of CF in patients 6 years of age and older who have a *G551D* mutation in the *CFTR* gene. The estimated prevalence of the *G551D* mutation is approximately 2374 patients globally. Based on 2010 data, the CF Trust has enrolled 432 patients with the *G551D* mutation and the CF Foundation has enrolled 1035 patients with the *G551D* mutation.^{1,2} By working with these patient registries, we expect to be able to analyse more than half of the *G551D* patients in the world. Assuming that most *G551D* patients are indicated for treatment with ivacaftor and will receive treatment, the number of patients analysed is expected to be sufficient to achieve the objectives of the study.

The power to detect a difference in death rates between the Ivacaftor Cohort and the Comparator Cohort are presented in the table below. The death rate in the unexposed group, 103 of 9385 (0.011), was obtained from the 2010 UK Trust Annual Report and is shown below as Proportion 1. Proportion 2, the death rate in the Ivacaftor Cohort, is varied between 138 in 10,000 (0.0138) to 440 in 10,000 (0.0440).

Table 6 Power Calculations for Detecting Differences in Death Rates

Relative Risk	Proportion 1	Proportion 2	Alpha	Power (N Exposed = 432 ^a)	Power (N Exposed = 1035 ^b)
1.25	0.011	0.0138	0.1	0.111	0.180
1.5	0.011	0.0165	0.1	0.190	0.347
1.75	0.011	0.0193	0.1	0.287	0.534
2	0.011	0.0220	0.1	0.393	0.703
2.25	0.011	0.0248	0.1	0.501	0.829
2.5	0.011	0.0275	0.1	0.604	0.911
2.75	0.011	0.0303	0.1	0.695	0.958
3	0.011	0.0330	0.1	0.772	0.981
3.25	0.011	0.0358	0.1	0.834	0.992
3.5	0.011	0.0385	0.1	0.882	0.997
3.75	0.011	0.0413	0.1	0.919	0.999
4	0.011	0.0440	0.1	0.945	1.000

Note: Power is from a single-sided Fisher exact test of 2 proportions, with alpha = 0.1, assuming equal N per group (Ivacaftor Cohort and Comparator Cohort). Because the number of patients exposed is based on the "best-case scenario" (i.e., all eligible patients receiving ivacaftor), the power is likely higher than actual.

^a CF Trust

^b CF Foundation

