9.1.1 Study Population

The Ivacaftor Cohort will include all patients who have been treated with ivacaftor and are enrolled in the CF Trust or CF Foundation patient registries. The Comparator Cohort will include patients who have never been exposed to ivacaftor and are matched on age group, *CFTR* genotype class, and sex (see Section 9.2.4) to patients in the Ivacaftor Cohort.

The Ivacaftor Pregnancy Study Cohort will include all female patients who have ivacaftor exposure in the analysis year and are enrolled in the CF Trust or CF Foundation patient registries. The Comparator Pregnancy Study Cohort will include female patients who have never been exposed to ivacaftor and are matched on *CFTR* genotype class to patients in the Ivacaftor Pregnancy Study Cohort (see Section 9.2.4).

The Comparator and Comparator Pregnancy Study Cohorts will be identified for each registry's Ivacaftor and Ivacaftor Pregnancy Study Cohorts, respectively, at a ratio of m:1, where m is the maximum number of matches available.

The Historical Cohort will include patients who have the *G551D-CFTR* mutation, were enrolled in the patient registries before ivacaftor was available in clinical studies and commercially in the US and the UK (i.e., 2008), and were never exposed to ivacaftor.

The Drug Utilisation Cohort will include all patients who have ever been treated with ivacaftor.

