9.3.4 Statistical Analyses

Data analyses will be performed by the CF Trust and CF Foundation to meet the study objectives. The results of the annual analyses will be reported in the study report.

The primary objectives of this study are to evaluate long-term safety, pregnancy outcomes, drug utilisation, and CF disease progression in patients treated with ivacaftor. Descriptive statistics will be calculated for all endpoints. All safety, pregnancy, and CF disease progression endpoints will be compared between the Ivacaftor and Comparator Cohorts or between the Ivacaftor Pregnancy and Comparator Pregnancy Cohorts. Safety and pregnancy outcomes will also be described for the Historical Cohort. Annual incidence rates will be calculated for safety outcomes (Objective 1). Crude relative risks or risk difference with 95% confidence intervals will be calculated for some outcomes, as appropriate. Statistical modelling with adjustment for confounders and effect modifiers will be conducted, as possible, due to the likely sparse data. Identification of confounders and effect modifiers will be performed using stratified analyses. Each annual report will include the patient data from the previous calendar year (e.g., annual cross-sectional analysis). Longitudinal analyses will be included, as appropriate, in the final report.

This section presents a summary of the planned statistical analyses for this study (see [Stand-alone Document 4](#) listed in Annex 1. List of Stand-alone Documents). A detailed

analysis plan will be presented in a statistical analysis plan. A summary of the comparisons to be made for each objective is provided in Table 5.

Table 5 Comparisons by Primary Objective

Objective	Setting	Cohorts Included	Comparisons
1. To evaluate the long-term safety of ivacaftor in patients with CF	UK, US	Ivacaftor; Comparator; Historical	
 Comparison of long-term safety between the Ivacaftor Cohort (ivacaftor-treated patients) and the Comparator Cohort (concurrent nonexposed patients) to include relative risks or risk differences Descriptive statistics for the Historical Cohort (historical nonexposed patients) will be available for comparison to the Ivacaftor Cohort (ivacaftor-treated patients). Comparisons to be based on 95% confidence intervals.

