The use of a Historical Cohort may also introduce bias in several ways. Data from a Historical Cohort are, by definition, different from the Comparator Cohort (selected from the same period as the Ivacaftor Cohort) because the CF care (e.g., medications, nonpharmacologic therapies, and treatment guidelines) have changed over time. Additionally, because the majority of patients with the *G551D* mutation are likely to be currently receiving ivacaftor, the Historical Cohort is likely to comprise the same patients, but at a different disease state (e.g., higher lung function, fewer clinical signs, and symptoms). The data fields for the registries are also modified slightly over time, limiting the ability to directly compare data from the Historical Cohort with those of cohorts based on more recent time periods.

Limitations on power and sample size

The number of patients included in annual analyses will be dependent on the use of ivacaftor amongst patients in the registries. As of 2010, the enrollment of patients with the *G551D-CFTR* mutation is 432 in the CF Trust and 1035 in the CF Foundation.^{1,2} Therefore, the power to detect differences in the study endpoints is limited. Whilst we explored the study power for detecting differences in mortality, the study is powered to detect 2- to 3-fold differences between study cohorts. One method to increase power would be to combine data from individual patient registries. Combining data sources was previously considered by the leadership of the patient registries in the UK and US independent of this study protocol, and they advised that previous pooled analysis has been limited to matching at the encounter level and methods for combining annual data have not been established. Throughout the conduct of the study, the feasibility of combining annual registry data will be further explored.

Limitations on the analyses for prior hypotheses

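### Table 6's power inputs (one-sided alpha 0.10, 1:1, one year) do not match the planned 95% CI, m:1 analysis, and the 2- to 3-fold statement in 9.9 is not supported for the UK registry

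*Protocol*

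**What the plan says.** Section 9.5 takes its reference mortality from one year of UK registry data: "The death rate in the unexposed group, 103 of 9385 (0.011), was obtained from the 2010 UK Trust Annual Report". The numbers exposed are 432 (CF Trust) and 1035 (CF Foundation), on the assumption that all eligible patients are treated. The note to Table 6 defines the calculation: "Power is from a single-sided Fisher exact test of 2 proportions, with alpha = 0.1, assuming equal N per group". It adds that power is likely to be lower in practice because the numbers are a best case.

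Two rows matter most. Their columns are relative risk, the two proportions, alpha, UK power and US power:

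- RR 2: "2 0.011 0.0220 0.1 0.393 0.703"
- RR 3: "3 0.011 0.0330 0.1 0.772 0.981"

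Section 9.9, under the limitations on power and sample size, first says that power is limited and then that "the study is powered to detect 2- to 3-fold differences between study cohorts". It does not separate the registries, and no target power is stated anywhere.

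The planned analysis is described elsewhere. Section 9.3.4: "Crude relative risks or risk difference with 95% confidence intervals will be calculated for some outcomes, as appropriate". Table 5 also refers to 95% confidence intervals for Objective 1. Section 9.1.1 has comparators identified for each registry "at a ratio of m:1, where m is the maximum number of matches available". Section 9.2.6 analyses each registry separately.

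**The concern.** A 95% confidence interval that excludes 1 on the side of harm corresponds to a one-sided test at 0.025. Table 6 uses one-sided 0.10, which corresponds to an 80% interval, so on this count it overstates power. It also assumes one comparator per treated patient where the plan takes as many as can be found, and on this count it understates power whenever m exceeds 1. The table therefore describes neither the planned analysis nor a clear bound on it.

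The sentence in 9.9 is the one most likely to be carried into reports. A reader who meets a null yearly mortality comparison in the UK registry, and has been told that the study is powered for 2- to 3-fold differences, could take a doubling of mortality as unlikely. Table 6 itself gives a 39% chance of detecting one.

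**Working it through.** **Inputs (Protocol).** Comparator death rate p1 = 103/9385 = 0.01097, rounded to 0.011 (9.5). Rate in the Ivacaftor Cohort p2 = RR × 0.011. Exposed n = 432 (UK) and 1035 (US) (9.5, 9.9). Planned interval 95% (9.3.4). Matching m:1 with m not fixed (9.1.1), so m = 1, 5 and 10 are assumed here.

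**Expected deaths in one year at the reference rate.** UK 432 × 0.011 = 4.8; US 1035 × 0.011 = 11.4.

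**Method.** Exact power of the one-sided Fisher test: sum Bin(x1; m·n, p1) × Bin(x2; n, p2) over all pairs (x1, x2) whose hypergeometric upper-tail p-value is at most alpha.

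**Step 1: reproduce Table 6** (alpha 0.10, m = 1).

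| RR | UK Table 6 | UK recomputed | US Table 6 | US recomputed |
|---|---|---|---|---|
| 2 | 0.393 | 0.386 | 0.703 | 0.706 |
| 2.25 | 0.501 | 0.495 | 0.829 | 0.832 |
| 2.5 | 0.604 | 0.598 | 0.911 | 0.913 |
| 3 | 0.772 | 0.769 | 0.981 | 0.982 |
| 3.25 | 0.834 | 0.832 | 0.992 | 0.993 |

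All 24 cells agree within 0.01, so the table has no arithmetic error.

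**Step 2: set Table 6 against the statement in 9.9.** Over RR 2 to 3, UK power runs from 0.393 to 0.772 and first passes 0.80 at RR 3.25. US power is 0.703 at RR 2, passes 0.80 at RR 2.25 (0.829) and is 0.981 at RR 3.

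**Step 3: replace alpha and allocation by the planned ones** (one-sided 0.025, the harm side of a 95% CI; one year; every eligible patient treated).

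| m | UK RR 2 | UK RR 3 | US RR 2 | US RR 3 | RR at 80% power, UK | RR at 80% power, US |
|---|---|---|---|---|---|---|
| 1 | 0.167 | 0.533 | 0.438 | 0.920 | 3.86 | 2.62 |
| 5 | 0.342 | 0.807 | 0.703 | 0.993 | 2.98 | 2.16 |
| 10 | 0.387 | 0.850 | 0.747 | 0.996 | 2.84 | 2.08 |

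**Step 4: check against the interval itself.** The power that a 95% log relative-risk interval lies above 1 is somewhat higher. At m = 1 it is 0.19/0.57 (UK, RR 2 / RR 3) and 0.49/0.94 (US); at m = 5, 0.44/0.87 and 0.76/1.00; at m = 10, 0.49/0.90 and 0.81/1.00. The RR at 80% power is then 3.74, 2.76 and 2.64 (UK) and 2.54, 2.06 and 2.00 (US) for m = 1, 5 and 10.

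**Step 5: direction of the two mismatches (UK, Fisher).** At RR 2, going from alpha 0.10 to 0.025 at m = 1 lowers power from 0.386 to 0.167; going from m = 1 to m = 10 at alpha 0.025 brings it back to 0.387. At RR 3 the same steps give 0.769, 0.533 and 0.850.

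**Step 6: sensitivity.** If 70% of eligible patients are treated (assumption; n = 302 and 725), the log relative-risk interval at m = 5 gives 0.35/0.75 (UK) and 0.63/0.97 (US) at RR 2 / RR 3. In the other direction, UK ivacaftor use is recorded only from 2013 (Table 2, footnote b), so the 2013 to 2016 data give at most 4 × 432 = 1728 person-years. Fisher power at RR 2 on that total, one-sided 0.025, is 0.68 at m = 1 and 0.925 at m = 10, assuming full and constant uptake.

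**The case against.** The case for leaving the text alone has weight. Table 6 states its test, alpha and allocation openly and is computed correctly. The primary objectives carry no prior hypotheses (8.3), the numbers are called a best case (9.5), and 9.9 admits limited power immediately before the disputed sentence. Registry size fixes the sample, so no design decision hangs on the table. Longitudinal analyses are already planned for the final report (9.2.6, 9.3.4), and section 11 promises a review of safety over the full study period.

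Those points stand, and they limit the finding. Three stronger readings are tempting, and the documents support none of them:

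- A reader might infer that the study falls short of 2- to 3-fold differences altogether. It does not: the US registry passes 80% from RR 2.25 in Table 6, and with high m the planned analysis comes close to the statement in both registries.
- A reader might infer that the lenient alpha makes Table 6 too optimistic overall. At m = 10 the UK figure at RR 2 is almost unchanged, and at RR 3 it is higher than the table's.
- A reader might infer that the UK registry would miss a doubling of mortality more often than not however the calculation is done. That is true of the one-year 95% CI comparisons calculated here, with m up to 10. It is false for four cumulated years (0.68 to 0.925), and for one year at alpha 0.10 with m = 3 (0.54).

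What the objection does not remove is that none of the caveats discloses the mismatch in alpha or matching, and that the sentence in 9.9 is unqualified while Table 6 gives the UK 39% to 77% over the range it names.

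**Conclusion.** The point holds as a mismatch of power assumptions, together with one sentence that Table 6 does not support for the UK. It is not an arithmetic error. For a one-year 95% CI comparison, the RR detectable with 80% power runs from 3.86 (m = 1) to 2.84 (m = 10) in the UK and from 2.62 to 2.08 in the US by Fisher; the log relative-risk interval gives slightly smaller values. At m of about 5 to 10, roughly 2-fold in the US and just under 3-fold in the UK is a fair description.

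This rests on a death rate of 0.011 in both registries, full uptake, independent observations without allowance for the matching, and assumed values of m. The 80% benchmark is a convention applied here, not a protocol target. Correction is worthwhile because it is cheap and the figures are there to be relied on, but no conduct of the study depends on it.

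**What to change.** 1. In 9.5, recompute Table 6 for each registry for the planned two-sided 95% confidence interval at stated values of m (for example 1, 5 and 10), keeping the best-case note and preferably adding a row for lower uptake.
2. In 9.9, replace the 2- to 3-fold sentence with the relative risk that each registry can detect in one year at a stated power and a stated m.
3. Optionally, add the cumulative multi-year power for the final report, with its uptake assumption stated.

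The cost is one recalculated table and one or two sentences. The stated one-year power will look less favourable at low m. No patients, data or analyses are added.
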